11.2.4. Abnormal Urinalyses That Require Additional Evaluation

Subjects who develop any of the following abnormal urine laboratory values must have the test repeated 2 weeks later:

- urinary casts (other than hyaline casts)
- glycosuria (trace or greater) in the setting of normal serum glucose

If the abnormality persists on retesting, then the subject should be fully investigated for possible causes and referred for evaluation by a nephrologist if appropriate in the opinion of the Investigator.

Subjects who demonstrate 1+ or greater proteinuria on a urine dipstick (and do not have a documented history of prior benign proteinuria) should have a spot protein/creatinine ratio (on AM void). If the spot protein/creatinine ratio is >0.2 mg/mg, then the subject should be fully investigated for possible causes and referred for evaluation by a nephrologist if appropriate in the opinion of the Investigator.

11.2.5. Treatment Schedule for Subjects With Abnormal Lymphocyte Count

11.2.5.1. Schedule for Subjects With Lymphocyte Count $<500/\text{mm}^3$

BG00012 must be permanently discontinued when the lymphocyte count meets the threshold limits defined in [Table 5](#).

CONFIDENTIAL

The information contained herein may not be used, disclosed, or published without the written consent of Biogen MA Inc.

Table 5: Lymphocyte Count Criteria Requiring Permanent Discontinuation of BG00012 Treatment

Laboratory Parameter	Laboratory Result	Required Action
Lymphocyte count	<500/mm ³	The Investigator should repeat the test as soon as possible. If retest confirms that lymphocyte count is <500/mm ³ , lymphocyte count should be closely monitored (at least every 4 weeks). If lymphocyte count is <500/mm ³ for more than 6 months, study treatment must be permanently discontinued.

If study treatment is permanently discontinued due to lymphocyte count <500/mm³, subjects may continue protocol-required tests and assessments and also undergo lymphocyte follow-up every 4 weeks for 24 weeks and then every 3 months (**unless clinically indicated more often or at the Investigator's discretion**) until the lymphocyte count is \geq LLN or for 52 weeks after the last dose, or until one of the following occurs: 1) the subject continues on commercial BG00012 following study withdrawal/completion, or 2) the subject is initiated on another MS disease-modifying therapy [see [Table 2](#)]. During the lymphocyte follow-up, if the lymphocyte count does not recover to above LLN after 24 weeks, the treating neurologist should contact the Medical Monitor.

11.2.5.2. Schedule for Subjects Who Complete, Temporarily Withhold, or Permanently Discontinue Study Treatment for Any Reason and Have a Lymphocyte Count <LLN

Subjects who complete the 96-week treatment period and who have a lymphocyte count <LLN will be followed every 4 weeks for 24 weeks and then every 3 months (**unless clinically indicated more often or at the Investigator's discretion**) until the lymphocyte count is \geq LLN or for 52 weeks after the last dose, or until one of the following occurs: 1) the subject continues on commercial BG00012 following study withdrawal/completion, or 2) the subject is initiated on another MS disease-modifying therapy. During the lymphocyte follow-up, if the lymphocyte count does not recover to above LLN after 24 weeks, the treating neurologist should contact the Medical Monitor.

[figure not shown]
Subjects who temporarily withhold or permanently discontinue study treatment for any reason (see [Section 10.1](#)) and who have a lymphocyte count <LLN will continue protocol-required tests and assessments and also undergo lymphocyte follow-up every 4 weeks for 24 weeks and then every 3 months (**unless clinically indicated more often or at the Investigator's discretion**) until the lymphocyte count is \geq LLN or for 52 weeks after the last dose, or until one of the following occurs: 1) the subject continues on commercial BG00012 following study withdrawal/completion, or 2) the subject is initiated on another MS disease-modifying therapy [see [Table 4](#)]. During the lymphocyte follow-up, if the lymphocyte count does not recover to above LLN after 24 weeks, the treating neurologist should contact the Medical Monitor.

CONFIDENTIAL

The information contained herein may not be used, disclosed, or published without the written consent of Biogen MA Inc.

See [Figure 2](#) for a schedule for subjects who complete, temporarily withhold, or permanently discontinue study treatment for any reason and who have a lymphocyte count <LLN.

Figure 2: Schedule for Subjects who Complete, Temporarily Withhold, or Permanently Discontinue Study Treatment for Any Reason and Have a Lymphocyte Count <LLN

LLN = lower limit of normal.

11.2.6. Dosage Reductions

Dosage reduction will be allowed only for subjects **who are unable to tolerate BG00012 treatment due to flushing and/or GI disturbances** (dosage reductions will not be allowed for abnormal laboratory values; for management of abnormal laboratory values, see Sections [11.2.1](#), [11.2.2](#), and [11.2.3](#)). Subjects who do not tolerate BG00012 treatment will reduce their dosage by taking one 120-mg capsule BID for up to 4 weeks. Within 4 weeks at the reduced dosage, subjects will resume taking the full dose of 240 mg (two 120-mg capsules) BID. If the subject is still unable to tolerate BG00012 treatment at the 240-mg BID dose, the subject may continue in the study taking the 120-mg BID dose.

11.3. Precautions

Medications for the treatment of severe hypersensitivity reactions (e.g., epinephrine for subcutaneous injections, diphenhydramine for injection) should be available for immediate use.

See the DHA for detailed instructions.

CONFIDENTIAL

The information contained herein may not be used, disclosed, or published without the written consent of Biogen MA Inc.

11.4. Compliance

Compliance with treatment dosing is to be monitored and recorded by site staff. Compliance for BG00012 will be monitored by capsule count and captured in the eCRF.

11.5. Concomitant Therapy and Procedures

11.5.1. Concomitant Therapy

A concomitant therapy is any drug or substance administered between the Baseline Visit and the Safety Follow-Up Visit.

11.5.1.1. Allowed Concomitant Therapy

Symptomatic therapy, such as treatment for spasticity, depression, or fatigue, is not restricted but should be consistent for the duration of the study.

Subjects should be instructed not to start taking any new medications, including nonprescribed drugs, unless they have received permission from the Investigator.

11.5.1.2. Disallowed Concomitant Therapy

Concomitant treatment with any of the following is not allowed while receiving study treatment, unless approved by the Medical Monitor, or as otherwise described in this protocol:

- Any alternative drug treatments directed toward the treatment of MS, such as immunomodulatory treatments (including but not limited to, interferon-beta, glatiramer acetate, natalizumab, fingolimod, teriflunomide, alemtuzumab, mitoxantrone, mycophenolate mofetil, laquinimod, cyclophosphamide, methotrexate, azathioprine, cyclosporine, etc.) and 4-aminopyridine or related products with the exception of acute management of protocol-defined relapse (as described in Section 11.5.2).
- Any investigational product, including investigational symptomatic therapies for MS and investigational therapies for non-MS indications.
- Any systemic steroid therapy including but not limited to, oral corticosteroids (e.g., prednisone) or periodic (e.g., monthly) treatment with IVMP, except for protocol-defined treatment of relapses as described in Section 11.5.2. Steroids that are administered by nonsystemic routes (e.g., topical, inhaled) are allowed.
- Total lymphoid irradiation, cladribine, T-cell or T-cell receptor vaccination, any therapeutic monoclonal antibody, intravenous (IV) immunoglobulin, plasmapheresis, or cytapheresis.

Subjects who receive any of these restricted medications without approval from the Biogen Medical Director(s) will be required to permanently discontinue study treatment and will be withdrawn from the study as outlined in Section 10.2.

CONFIDENTIAL

The information contained herein may not be used, disclosed, or published without the written consent of Biogen MA Inc.

Use of the concomitant therapies or procedures defined above must be recorded on the subject's eCRF, according to the instructions for eCRF completion. AEs related to the administration of these therapies or procedures must be documented on the appropriate eCRF.

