7.2.3. Follow-Up

Subjects are to return to the study site for a follow-up visit 4 weeks after their last treatment visit (Visit 10 at Week 96 [± 5 days]).

Subjects who withdraw prematurely from the study will complete the Early Withdrawal Visit, which should be conducted as soon as possible and no later than 4 weeks after the subject's last dose of study treatment. Subjects who withdraw prematurely should be encouraged to complete the Safety Follow-Up Visit 4 weeks after the last dose of study treatment.

Subjects who complete, temporarily withhold, or permanently discontinue study treatment for any reason and have a lymphocyte count less than the lower limit of normal (LLN) will be followed every 4 weeks for 24 weeks and then every 3 months (**unless clinically indicated more often or at the Investigator's discretion**) until the lymphocyte count is \geq LLN or for 52 weeks after the last dose, or until one of the following occurs: 1) the subject continues on commercial BG00012 following study withdrawal/completion, or 2) the subject is initiated on another MS disease-modifying therapy.

CONFIDENTIAL

The information contained herein may not be used, disclosed, or published without the written consent of
Biogen MA Inc.

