10. DISCONTINUATION OF STUDY TREATMENT AND/OR WITHDRAWAL OF SUBJECTS FROM THE STUDY

10.1. Discontinuation of Study Treatment

A subject *must* permanently discontinue BG00012 for any of the following reasons:

- The subject becomes pregnant. Study treatment must be discontinued immediately. Report the pregnancy according to the instructions in Section [15.4.1](#).
- The subject experiences a medical emergency that necessitates permanent discontinuation of study treatment.
- The subject has lymphocyte count $<500/\text{mm}^3$ for 6 months as outlined in [Table 4](#) and [Table 5](#).
- The subject experiences a protocol-specified change in laboratory values that necessitates permanent discontinuation of treatment as outlined in [Table 3](#) and [Table 4](#).
- The subject cannot tolerate study treatment.
- The subject receives any of the disallowed concomitant medications for this study.
- The subject or subject's parent/legal guardian desires to discontinue treatment.
- At the discretion of the Investigator for medical reasons or for noncompliance.

The reason for discontinuation of study treatment must be recorded in the subject's eCRF.

Subjects who discontinue treatment may remain in the study and continue protocol-required tests and assessments.

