10.2. Withdrawal of Subjects From Study

Subjects must be withdrawn from the study for any one of the following reasons:

- The subject or the subject's parent/guardian withdraws consent.
- The subject enrolls into another interventional clinical study.
- The subject is unwilling or unable to comply with the protocol.

The reason for the subject's withdrawal from the study must be recorded in the subject's eCRF.

CONFIDENTIAL

The information contained herein may not be used, disclosed, or published without the written consent of
Biogen MA Inc.

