11.5.3. Treatment of Relapses on Scheduled or Unscheduled Visits

The only protocol-approved treatment for relapse in this study is either 3 or 5 days with IVMP, up to 1000 mg/day. IVMP can be given once a day or in divided doses. Subjects may also refuse relapse treatment. Any deviations from this recommended treatment must first be discussed with the Biogen Medical Director or designee.

Study treatment dosing is to continue uninterrupted during IVMP treatment.

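### Section 11.5.1.2 withdraws subjects from the study for unapproved restricted therapy, while 10.1 only stops their treatment; following 11.5.1.2 gives up outcome follow-up that the study could keep

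*Protocol*

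**What the plan says.** All references are to protocol version 3.0 unless the SAP is named.

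- **Section 11.5.1.2** lists the restricted therapies: other MS drugs, investigational products, systemic steroids outside protocol-defined relapse treatment, and several immune therapies and procedures. Concomitant use "is not allowed while receiving study treatment, unless approved by the Medical Monitor, or as otherwise described in this protocol". A subject who receives one without approval "will be required to permanently discontinue study treatment and will be withdrawn from the study as outlined in Section 10.2".
- **Section 10.2** gives three reasons for withdrawal from the study: withdrawn consent, entry into another interventional study, and "The subject is unwilling or unable to comply with the protocol". It does not mention restricted therapy.
- **Section 10.1** lists reasons for permanently stopping BG00012. One is: "The subject receives any of the disallowed concomitant medications for this study". It closes with: "Subjects who discontinue treatment may remain in the study and continue protocol-required tests and assessments".
- **Section 11.5.3** defines the permitted relapse treatment: "The only protocol-approved treatment for relapse in this study is either 3 or 5 days with IVMP, up to 1000 mg/day". Deviations must first be discussed with the sponsor's Medical Director or designee.
- **Section 7.2.3** covers what follows withdrawal: "Subjects who withdraw prematurely from the study will complete the Early Withdrawal Visit", no later than 4 weeks after the last dose. The Safety Follow-Up Visit is only encouraged for these subjects, and Table 1 has no EDSS or MRI at that visit.
- **Table 2** keeps treatment discontinuation and study withdrawal apart as two different events (footnote 2).

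**The concern.** The same event has two different consequences. Under 10.1, a subject who takes a disallowed drug stops BG00012 and may stay. Under 11.5.1.2, the same subject leaves the study, on the authority of a section that does not name the event. Two sites could handle identical cases differently and both point to the protocol.

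The design consequence matters more than the cross-reference. One secondary objective in Section 6.2 is to describe long-term MS outcomes in subjects who completed Study 109MS202, and it is not limited to time on drug. A subject who adds another MS drug, or whose relapse is treated with oral steroids without approval, may well have active disease. Withdrawal ends the collection of later relapses, EDSS and lesion counts in such a subject. Other subjects who stop BG00012, for example for intolerance or a laboratory criterion, may continue.

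**Working it through.** **1. The texts side by side.** The event is unapproved restricted therapy while on BG00012.

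| Section | Treatment | Study participation |
|---|---|---|
| 10.1 | Stop permanently | May remain |
| 10.2 | Not addressed | Event not named; non-compliance is the nearest reason |
| 11.5.1.2 | Stop permanently | Withdraw, citing 10.2 |
| 11.2.5.2, lymphocytes below LLN | Stopped for any 10.1 reason | Continue protocol-required assessments |

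The last row adds a second conflict. A subject with low lymphocytes who took an unapproved steroid is kept by 11.2.5.2 and removed by 11.5.1.2. Section 11.5.1.2 also cites 11.5.2 for relapse treatment, which is in 11.5.3, so its cross-references need checking in any case.

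**2. Inputs for the loss per subject.**
- Post-baseline EDSS (Table 1): Weeks 12, 24, 36, 48, 72 and 96, six in all.
- Post-baseline MRI (Table 1): Weeks 16, 24, 64 and 72, four in all.
- Withdrawal visit: between L and L + 4 weeks, where L is the week of the last dose. It includes an EDSS, and an MRI unless one was done in the last 30 days (Table 2, footnote 10). No MRI may be done within 30 days of a steroid course (footnote 9).
- Relapses: Table 1 has no scheduled relapse assessment. Relapses are assessed at unscheduled visits prompted by symptoms (Section 7.3), so the loss is observation time.
- The values of L are assumed. The comparison is full attendance to Week 96, so the results are maxima for one subject.

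**3. Relapse observation and scheduled assessments lost.** Weeks lost run from 96 − (L + 4) to 96 − L.

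| Last dose | Relapse weeks lost | Scheduled EDSS lost | Scheduled MRI lost |
|---|---|---|---|
| Week 24 | 68 to 72 | 4 of 6 (Weeks 36, 48, 72, 96) | 2 of 4 (Weeks 64, 72) |
| Week 48 | 96 − 52 = 44 to 96 − 48 = 48 | 2 of 6 (Weeks 72, 96) | 2 of 4 (Weeks 64, 72) |
| Week 72 | 20 to 24 | 1 of 6 (Week 96) | 0 of 4 |

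For Week 48 the loss is 44/52 = 0.85 to 48/52 = 0.92 years.

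**4. Offset from the withdrawal visit, last dose Week 48.** One EDSS is added, so the net EDSS loss is 2 − 1 = 1. If that visit falls on the same day as the Week 48 visit, nothing is added and the net loss is 2. The last scheduled scan, at Week 24, is then 24 to 28 weeks (168 to 196 days) old, so a scan is due and the net MRI loss is 2 − 1 = 1. If a steroid course was given in the prior 30 days, the scan is barred and the loss stays at 2. This can easily happen when steroids triggered the withdrawal, because the visit is at most 28 days after the last dose.

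**5. Confirmation of EDSS progression, last dose Week 48.** Worsening must be sustained for 24 weeks. With the last EDSS no later than Week 52, it must first be seen by Week 52 − 24 = 28. Worsening first seen at Week 12 or 24 can be confirmed; worsening first seen at Week 36 or 48 cannot. With full follow-up, the Week 72 and 96 visits would allow it.

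**6. Does the SAP recover any of this?** SAP 6.1.7 assigns an early withdrawal visit to the next scheduled visit only within a ±5-day window. The next visit after Week 48 is Week 60, at least 60 − 52 = 8 weeks later, so the rule does not move the data forward. SAP 6.2.2 has no rule for data after a change of MS therapy.

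**The case against.** The strongest defence is that there is no true contradiction. Section 10.1 permits discontinuers to stay but does not promise it. Section 11.5.1.2 is the more specific rule, and the non-compliance reason in 10.2 is a plausible target for its reference. On that reading 11.5.1.2 controls and is a deliberate choice. This is a fair reading, and it reduces the textual conflict to a clarification. It does not remove the loss of outcome data, and it leaves the clash with 11.2.5.2.

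The rule is also narrow. It applies only during BG00012 treatment and only without approval, and 11.5.3 offers a route to agree other relapse treatment in advance. That stands, and it is why the effect is probably small.

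Several stronger readings are tempting but not supported:
- **All subjects who switch therapy are lost.** A subject who stops BG00012 first and then switches is outside the rule.
- **Follow-up always ends at one visit.** Section 11.2.5.2 keeps discontinuers with lymphocytes below LLN in assessments.
- **The secondary estimates are biased in a known direction.** The documents give no expected number of such subjects and no basis for a direction.
- **Keeping these subjects would add 44 weeks of adverse events under another drug, because SAP 6.3.2.2 sets no end date.** Section 15.3.1 records AEs only to the Safety Follow-Up Visit, which the Synopsis places 4 weeks after the last dose. Table 1 and 7.2.3 leave that timing less than clear, but it concerns every retained discontinuer and is a separate matter.

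**Conclusion.** The point holds as an avoidable loss of follow-up together with an unreconciled set of rules. For a last dose at Week 48, the maximum loss per subject is 44 to 48 weeks of relapse observation, the EDSS at Weeks 72 and 96, and the MRI at Weeks 64 and 72, less what the withdrawal visit adds back. Worsening first seen at Week 36 or 48 cannot be confirmed.

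These figures assume that the subject would otherwise have attended every visit, and they use nominal visit weeks. The visit windows matter at the margin: Week 72 to Week 96 is 168 days nominally but 158 to 178 days with ±5 days at each end, so confirmation of worsening first seen at Week 72 is not certain even with full follow-up.

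No study-level size can be given. ARR stays computable, and the proportion relapsing changes only if a subject's first relapse comes after withdrawal. The affected endpoints are secondary and descriptive, and the effect is probably small. A reader might infer harm to the primary endpoint, but BG00012 stops under either section, so the conflict does not change it.

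**What to change.** In protocol Section 11.5.1.2, require permanent discontinuation of BG00012 only, cite Section 10.1, and state that these subjects stay in scheduled follow-up unless a reason listed in 10.2 applies. If the sponsor does intend withdrawal, the minimum is to name the reason in 10.2 and reconcile 10.1 and 11.2.5.2 with it.

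In SAP 6.2.2, present the efficacy summaries (MRI lesions, ARR, proportion relapsing, EDSS and confirmed progression) both with and without data collected after the start of another MS therapy. The retained data then serve the long-term outcomes objective without being mistaken for results on BG00012.

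The cost is a protocol amendment, with ethics committee approval where Section 19.3 requires it, attendance at already scheduled visits by a few subjects, and a few extra descriptive tables.

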11.5.2. Concomitant Procedures

A concomitant procedure is any therapeutic intervention (e.g., surgery/biopsy, physical therapy) or diagnostic assessment (e.g., blood gas measurement, bacterial cultures) performed between the time the subject is enrolled in the study and the Final Study Visit.

The use of concomitant procedures must be recorded on the subject's eCRF, according to instructions for eCRF completion. AEs related to the administration of these procedures must be documented on the appropriate eCRF.

11.5.3. Treatment of Relapses on Scheduled or Unscheduled Visits

The only protocol-approved treatment for relapse in this study is either 3 or 5 days with IVMP, up to 1000 mg/day. IVMP can be given once a day or in divided doses. Subjects may also refuse relapse treatment. Any deviations from this recommended treatment must first be discussed with the Biogen Medical Director or designee.

Study treatment dosing is to continue uninterrupted during IVMP treatment.

11.6. Continuation of Treatment

There is no provision for additional courses of BG00012 provided by Biogen beyond the treatment period defined in this protocol.

If and when BG00012 is commercially available at the time the study treatment period is completed, subjects will be allowed to take commercial BG00012 during the Safety Follow-Up Period if deemed appropriate by product labeling and at the discretion of their treating physician.

CONFIDENTIAL

The information contained herein may not be used, disclosed, or published without the written consent of
Biogen MA Inc.

12. STUDY TREATMENT MANAGEMENT

Study site staff should follow the DHA for specific instructions on the handling, preparation, administration, and disposal of the study treatment. The DHA supersedes all other references (e.g., protocol).

Study treatment must be dispensed only by a pharmacist or appropriately qualified staff. Study treatment is to be dispensed only to subjects enrolled in this study.

12.1. BG00012

BG00012 is a drug product formulated as enteric-coated microtablets in gelatin capsules (blue and white) for oral administration. Each capsule contains 120 mg BG00012.

Excipients for the manufacturing of the enteric-coated microtablets include microcrystalline cellulose, croscarmellose sodium, talc, colloidal anhydrous silica (colloidal silicon dioxide), magnesium stearate, triethyl citrate, methacrylic acid-methyl methacrylate copolymer, methacrylic acid-ethyl acrylate copolymer, simethicone, sodium lauryl sulfate, and polysorbate 80. Excipients for the manufacturing of the capsule shell include gelatin, titanium dioxide, and indigotin.

The contents of the study treatment label will be in accordance with all applicable regulatory requirements. BG00012 should not be used after the expiration date.

